6.7.2 Exclusion criteria for subject/patient selection

Meeting one of the following exclusion criteria will not allow for inclusion of the patient.

Ophthalmic Exclusion Criteria in AT LEAST ONE EYE

- Far best-corrected visual acuity $\leq 2/10$;
- Severe blepharitis (grade 3 / 0-3 scale);
- Ocular rosacea;
- Severe Dry Eye associated to:
 - Eyelid malposition,
 - Corneal dystrophy,
 - Ocular neoplasia,
 - Filamentous keratitis,

- Corneal neovascularisation,
- Orbital radiotherapy.
- History of ocular trauma, ocular infection or ocular inflammation within the last 3 months;
- History of ocular allergy;
- History of uveitis;
- History of inflammatory corneal ulcer within the last 12 months;
- Glaucoma, ocular hypertension requiring glaucoma treatment.

Systemic/non Ophthalmic Exclusion Criteria

- Known or suspected hypersensitivity to one of the components of the Investigational Device or auxiliary products;
- History of active relevant systemic condition incompatible with the investigation or likely to interfere with the investigation results or the patient safety according to investigator judgment;
- Allergic rhinitis active or susceptible to reactivate during the investigation;
- Any other medical or surgical history, disorder or disease susceptible to require or to modify systemic medication during the investigation (systemic medication having to be stable within the three months before selection).

Specific Exclusion Criteria regarding Childbearing Potential Women

- Pregnancy or breastfeeding;
- Childbearing potential woman who is not using a reliable method of contraception (oral contraceptive, intra-uterine device, subcutaneous contraceptive implant, vaginal ring, patch) and is not surgically sterilised.

Exclusion Criteria Related to General Conditions

- Inability of patient to understand the investigation procedures or to give informed consent;
- Non-compliant patient (*e.g.*, not willing to attend a visit or completing the self-questionnaire; way of life interfering with compliance);
- Participation in this investigation at the same time as another clinical investigation;
- Participation in this investigation during the exclusion period of another clinical investigation;
- Patient previously randomised in this investigation;
- Patient being institutionalised because of legal or regulatory order, inmate of psychiatric wards, prison or state institutions, or employee of the investigation sites or of the sponsor's company;
- Patient not covered by the French government health care;
- Patient under guardianship/ward of court;

- Patient with previous, current prohibited listed treatment (or prohibited modification of treatment regimen, see Table 1, page 11).

6.7.3 Criteria and procedures for patient withdrawal or discontinuation

Patient should be withdrawn from the investigation if, in the opinion of the investigator, there is any situation or condition which puts the subject at significant risk. Any patient may voluntarily discontinue the investigation at any time he or she chooses (Declaration of Helsinki), without prejudice. The investigator may choose to discontinue a patient for reasons related to the investigation product (AE or unsatisfactory therapeutic response). In either event, details should be recorded in the e-CRF and reported separately.

Possible reasons for withdrawal include the following:

- AEs leading to discontinuation from the investigation;
- Treatment failure: the patient or the physician does not feel that the IMD has adequately relieved his/her symptoms;

In case of aggravation of dry eye syndrome or superficial keratitis, an adverse event form must be completed by the investigator and all the investigations planned at the final visit must be done (premature withdrawal visit). The investigator will prescribe the best appropriate treatment to the patient.

- Patient's request;
- Other reason.

If the patient is lost to follow-up, the investigator must contact his/her patient to obtain more information (by phone, fax, regular mail or email...).

If a patient discontinues prematurely the investigation, the investigator will perform all the investigations planned at the final visit and will prescribe the best appropriate treatment to the patient.

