Statistical method	
The aim of the study is to demonstrate the non - inferiority of T2259 with regard to Vismed® Multi in terms of performance.
 
The primary performance criterion is the change from baseline of total ocular staining grade in the worst eye on Day 35, evaluated using Oxford 0-15 grading scheme.
 
As the statistical hypothesis is the non-inferiority of T2259 with regard to Vismed® Multi, the main analysis of the primary criterion will be performed in the Per protocol population.
 
A total of 76 patients (i.e. 38 per treatment group) assume at least 90% power to establish the non-inferiority comparison on a one-sided two sample t-test with alpha=2.5 % basis (equivalent to a 95% two-sided confidence interval), assuming that the standard deviation is 2.5 and no difference between the 2 groups with a non-inferiority limit set at 2 for the change in total ocular staining grade.
 
Estimation of the standard deviation and determination of the non-inferiority limit are based upon data of previous studies and literature.
 
Concerning the non - inferiority limit, according to clinicians, a variation of 2 points in the total Oxford grade, which corresponds to a variation of less than 1 grade in the three areas (corneal, temporal and nasal), is considered as not clinically significant.
 
For taking into account approximately 15% of patients non-evaluable in Per protocol analysis (premature withdrawals without performance evaluation, patients with major protocol deviation), a total of 90 patients should be randomised in the study.

Sample size	90 randomised patients.										
Investigation Design	Multicentre, randomised study, investigator-masked, 2 parallel groups (T2259 versus Vismed® Multi) of 38 evaluable patients each.										
Investigation Duration	Run-in-period with preservative free artificial tears (Hydrabak®): from Day 1-10 or Day 1-7 to randomisation visit (Day 1) (one drop in each eye 3 to 6 times daily). 
 ▪ Treatment period: 84 ± 7 days ▪ Total study duration: maximum of 101 days 										

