6.2.1 Randomisation

A patient who has given his/her written informed consent and who is included in the study will be assigned a specific treatment number.

Random allocation of patients in the T2259 group or Vismed® Multi group will assure that all patient's known and unknown characteristics are similar and balanced between groups at the beginning of the study, avoiding the selection bias.

The randomisation code list stratified by site is generated by the CRO in charge of the statistics. Patients will be randomised on a 1:1 basis to T2259 or comparator product respectively. The IP will be allocated to the patients according to randomisation using an interactive response system (IWRS).

Randomisation will occur at the randomisation visit (Day 1; Visit 2) after all screening procedures have been performed and eligibility for the study confirmed. The patient who meets the eligibility criteria will be randomly assigned to treatment and associated to a randomisation number.

The treatment number should be recorded in patient's source documents and in the e-CRF.

During the visit 4 (Day 35), this investigator will allocate the same treatment number than he did at the randomisation visit.

The treatment number must be recorded in the patient's source document and the e-CRF.

If a discontinued patient needs to be replaced, the next available treatment number in the centre will be used.

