7.2 Definition of investigation sets

Full Analysis Set (FAS) will be composed of all randomised patients (according to ITT principle, i.e. analysed based on the initial treatment assignment), having used at least one dose of investigation medication and for whom at least one post-baseline performance evaluation will be available.

Per protocol set (PP) will be a subset of the FAS without major protocol deviation. The precise reasons for excluding patients from the PP set will be defined and documented before breaking the blind during the Blind Review Meeting.

Safety population will be composed of all patients exposed to the investigation drug, i.e. having used at least one administration of the investigation drug.

The **Eligible Eye** will be defined by following conditions:

- Oxford 0-15 score ≥ 4 and ≤ 9 AND;
- At least one of the following objective signs:
 - Schirmer test ≥ 3 mm/5 min and ≤ 9 mm/5 min,

Or

- Sum of 3 TBUT measurements ≤ 30 seconds.

For patients with both eligible eyes, the **Worst Eye** will be:

- Eye with the worst Oxford score;
- if same Oxford score in both eyes: eye with the worst Schirmer score;
- if same Oxford and Schirmer scores in both eyes: eye with the worst TBUT score;
- if same Oxford, Schirmer and TBUT scores in both eyes: right eye.

For patients with one eligible eye, the “worst eye” will be the eligible eye.

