5.2 Generalities for statistical analyses

After the database lock and the randomisation code release, the statistical analysis will be performed by the statistician of Axonal-Biostatem, using SAS® software v9.4 (GUIDE, SAS Institute, North Carolina, USA), according to this SAP.

Disposition and baseline characteristics will be presented overall (globally) and by treatment groups. Performance and safety assessments and exposure/compliance will be presented by treatment groups.

Continuous variables will be summarised using descriptive statistics (number of non-missing data (n), number of missing observations, mean, standard deviation (SD), median, lower quartile (Q1), upper quartile (Q3), minimum and maximum).

Except minimum and maximum, descriptive statistics will be presented with one more decimal than the recorded value.

To compare treatment groups for ordinal qualitative variables, Cochran-Mantel-Haenszel (CMH) test will be used stratified by baseline values (if mentioned), with modified ridit scores and “row mean score differ” option. To compare treatment group when variable will be quantitative, Student T-test will be used, when data distribution will be assumed as normal (Shapiro-Wilk test for normality). If it is not the case, Mann-Whitney Wilcoxon test will be preferred instead.

Quantitative parameters will be also compared between groups using ANCOVA model. Furthermore, the mean change from baseline in total staining grade in the worst eye at Day 35 will be compared between the two treatments based on the MMRM analysis, which assumes:

- Data are Missing At Random (MAR)
- All the available data provide the information about non-observed data
- The treatment effect assume that the withdrawn patients mimic those who continued

Assumptions underlying the ANCOVA (respectively MMRM for the sensitivity analysis) will be checked:

- A histogram of residuals will be plotted to check the assumption of normality
- The underlying assumptions of normality of residuals will also be checked by using Shapiro-Wilk test
- Normal probability plot and QQ-plot will be performed to check the assumption of normality
- Residuals will be plotted against predicted values to check the assumption of heteroscedasticity
- For ANCOVA models, Levene's test will also be performed to check the homogeneity of variances

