6.7 Performance analyses

6.7.1 Primary Performance Endpoint

Primary performance endpoint will be analysed only in the worst eye.

Descriptive tables will be produced presenting selection, baseline (D1), Day 8, Day 35 and Day 84 Oxford Total score and change from baseline for Oxford Total score at Day 8, Day 35 and Day 84.

Oxford grade at each visit and change from baseline at Day 8, Day 35 and Day 84 will be also described for each panel: temporal bulbar conjunctiva, corneal area and nasal bulbar conjunctiva.

The hypothesis of non-inferiority of T2259 compared to Vismed® Multi will be tested by calculating the bilateral 95% CI of the difference between groups (T2259 – Vismed® Multi) of the change from baseline of Oxford Total Score on Day 35. A two-way analysis of covariance (ANCOVA) model will be constructed using main effects of investigation product and baseline score as covariate. Adjusted means by investigation product will be presented as well as an estimate of the difference between adjusted means.

A 95% two-sided confidence interval, based on the ANCOVA model (2), will be computed for the difference of T2259 minus Vismed® Multi. If the upper bound is no higher than 2 points for the PP population, it will be concluded that the null hypothesis can be rejected and that T2259 is non-inferior to Vismed® Multi.

The result will be presented as follow:

Population	T2259 (N=XX)	Vismed® Multi (N=XX)	Difference T2259 – Vismed Multi	SE of Difference T2259 – Vismed Multi	95% CI
Day 1 (baseline) mean (SD)	X1	Y1			
Day 35 mean (SD)	X2	Y2			
Adjusted mean change (SE) between Day 1 and Day 35	[X2- X1]*(SE)	[Y2-Y1]*(SE)	[X2-X1] -[Y2-Y1]	SE	[Min - Max**]

* These values were expected as negative, meaning an improvement of the Oxford score.

** The upper bound indicates the maximal difference of change in disfavour of T2259.

This analysis will be performed firstly on the Per Protocol population on the observed data.

Same analysis will be performed on FAS population with imputation of values in case of missing data with LOCF technique (Day 8 or value in case of withdrawal) and without imputation (observed cases) for confirmation.

The country and the investigation product-by-country interaction will be explored as a secondary analysis prior to presenting the final model (1).

Same analysis as principal analysis (ANCOVA model) will be performed adjusted on possible impact of COVID-19 pandemic (3).

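### Early withdrawals for failure or an adverse event can have no Day 35 value in the deciding per-protocol analysis, and no planned analysis of the primary endpoint uses the reason for withdrawal

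*Protocol*

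**What the plan says.** **Withdrawal.** Protocol 6.7.3 lists adverse events and treatment failure among the reasons for withdrawal and also covers aggravation of the disease. "If a patient discontinues prematurely the investigation, the investigator will perform all the investigations planned at the final visit". It describes no assessment after that one.

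**Where the withdrawal score goes.** SAP 4.3 and 6.2 move it to the closest scheduled visit that is missing (Day 8, 35 or 84), and SAP 4.3 uses it in the analysis as that visit. SAP 2.1 instead points to the nearest scheduled visit that is not missing. Day 8 is optional in both documents.

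**Analyses of the primary endpoint.** SAP 6.7.1: "This analysis will be performed firstly on the Per Protocol population on the observed data". The conclusion rests on the PP upper bound. The FAS analysis is confirmatory and is run with LOCF (Day 8 or withdrawal value) and as observed cases. The FAS is defined "according to ITT principle, i.e. analysed based on the initial treatment assignment". The MMRM is a sensitivity analysis, for which SAP 5.2 states: "The treatment effect assume that the withdrawn patients mimic those who continued".

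**Reason for withdrawal.** SAP 6.2 tabulates it, with adverse event and lack of performance as categories. None of the primary-endpoint models in SAP 5.3 and 6.7.1 uses it.

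**The concern.** In a non-inferiority trial, patients who stop because a product failed them or was not tolerated are part of the evidence against it. If some of them are absent from the deciding comparison and are more numerous or worse off in the test arm, the estimated difference moves towards zero and the upper confidence bound moves away from the 2-point limit.

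The patients at issue are a defined subset: withdrawn for an adverse event or lack of performance, before about day 21.5, with no Day 8 visit. Their withdrawal grade exists but does not count at Day 35 in the PP or the FAS observed-case ANCOVA. No planned analysis asks what happens to the conclusion if these patients are counted as having done badly.

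**Working it through.** **1. Inputs from the plan** (Protocol synopsis; repeated in Protocol 7.5 and SAP 5.1)
- Test: "one-sided two sample t-test with alpha=2.5 % basis (equivalent to a 95% two-sided confidence interval").
- Size and power: "A total of 76 patients (i.e. 38 per treatment group) assume at least 90% power to establish the non-inferiority comparison".
- Assumptions: "assuming that the standard deviation is 2.5 and no difference between the 2 groups with a non-inferiority limit set at 2".
- Allocation (Protocol 6.2.1): "Patients will be randomised on a 1:1 basis to T2259 or comparator product respectively".

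**2. The plan's own figures.** SE = 2.5 × √(2/38) = 0.574, with 74 degrees of freedom. Power from the non-central t is 93.1%, so the stated lower bound of 90% is met. Inflation: 76/0.85 = 89.4, rounded up to 90, as stated. SAP 5.1 later reports 101 randomised to keep about 76 in PP: 1 − 76/101 = 24.8% non-evaluable against the planned 15%. It gives no split by arm or reason.

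**3. Who loses the Day 35 value.** The midpoint of Day 8 and Day 35 is (8 + 35)/2 = 21.5. For a withdrawal before Day 35:

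| Situation | Filed at (SAP 4.3, 6.2) | Day 35 value in PP and FAS observed cases |
|---|---|---|
| Day 8 visit held | Day 35 | yes |
| No Day 8 visit, after about day 21.5 | Day 35 | yes |
| No Day 8 visit, before about day 21.5 | Day 8 | **no** |

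Under the literal wording of SAP 2.1 the score could not go to Day 35 in any of these rows, because Day 35 is itself the missing visit.

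**4. Size of the bias.** Let f be the share of patients in an arm who fail before Day 35 and lack a Day 35 value, and d their deficit against the other patients (higher Oxford change = worse). The all-patient mean exceeds the observed mean by f × d, so

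bias towards T2259 = f(T2259) × d(T2259) − f(Vismed) × d(Vismed), which is (difference in f) × d when d is the same in both arms.

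The documents give neither f nor d. The assumed values are f = 8, 12 or 16% on T2259, 4% on Vismed Multi, and d = 2 or 4 points.

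**5. False-claim rate.** With a true all-patient difference of exactly 2, this is P(T > 1.993), where T is non-central t with 74 df and non-centrality bias/0.574. If half the failures have a Day 35 value, the bias roughly halves.

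| T2259 vs Vismed Multi | d | Bias, none has Day 35 | False claim | Bias, half have Day 35 | False claim |
|---|---|---|---|---|---|
| 8% vs 4% | 2 | 0.08 | 3.4% | 0.04 | 2.9% |
| 8% vs 4% | 4 | 0.16 | 4.6% | 0.08 | 3.4% |
| 12% vs 4% | 2 | 0.16 | 4.6% | 0.08 | 3.4% |
| 12% vs 4% | 4 | 0.32 | 7.9% | 0.16 | 4.6% |
| 16% vs 4% | 2 | 0.24 | 6.1% | 0.12 | 4.0% |
| 16% vs 4% | 4 | 0.48 | 12.8% | 0.24 | 6.1% |

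**6. Other directions.** Equal f and d give zero bias and 2.5%. Reversing the arms makes the bias negative: −0.08 gives 1.8% and −0.48 gives 0.3%. When the withdrawal score is used at Day 35 and reflects Day 35 status, simulation with 50 randomised per arm keeps the rate at 2.2-2.8%.

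**7. When it would matter.** The confidence-interval half-width is 1.993 × 0.574 = 1.14. With an observed difference of 0, a bias of 2 − 1.14 = 0.86 would be needed to reach the limit, more than any value above. The largest bias, 0.48, changes the conclusion only if the upper bound lies above 2 − 0.48 = 1.52.

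**The case against.** The case for the plan is substantial.

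- **LOCF uses the failing score.** Protocol 7.3.2 puts FAS with LOCF ahead of FAS observed cases, and it carries the patient's own withdrawal grade to Day 35, even when that grade is filed at Day 8. A reader might infer that no planned analysis counts a failure as a failure; that is not so. What stands is that the conclusion in SAP 6.7.1 is tied to PP and that LOCF takes no account of the reason. SAP 3.3 derives the safety set, and through it the FAS, from a treated-eye record at Day 35 or Day 84, narrower than the one-dose definition in SAP 6.1.2. Whether that removes early withdrawals depends on form coding that the documents do not show.
- **Many withdrawal scores do reach Day 35.** A reader might infer that everyone who stops is treated like a completer. The filing rule in SAP 4.3 and 6.2 contradicts this. Day 8 is held when someone thinks it necessary, so failing patients may be likelier to have it, and the affected group may be small.
- **The MMRM is not completer imputation.** It conditions on the score filed at Day 8, and its assumption is disclosed. It remains an assumption that nothing planned tests.
- **The direction is not given.** A reader might infer that the plan favours T2259. The documents give no withdrawal rates by arm, and the bias can be nil or reversed. Nor does the 24.8% non-evaluable share show a failure problem: it includes protocol deviations, and the SAP attributes the missing data partly to the pandemic.
- **Stopping and leaving.** Protocol 6.7.3 concerns discontinuing the investigation, and SAP 6.8.2 distinguishes product from study withdrawal, so the plan does not strictly equate them. Similarly, the ITT wording for the FAS concerns the arm in which a patient is analysed and promises no follow-up.

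**Conclusion.** The concern holds in a narrow form. Under SAP 4.3 and 6.2, patients withdrawn for an adverse event or lack of performance before about day 21.5 without a Day 8 visit have no Day 35 value in the deciding PP analysis or in FAS observed cases. The MMRM covers them only under missing at random, and the recorded reason is not used for the primary endpoint.

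The effect could favour non-inferiority only if such failures are more frequent or worse on T2259. Under the assumed rates and deficits, the false-claim rate at the margin is 3.4-12.8% as an upper range and about 2.9-6.1% if half the failures have a Day 35 value. The upper range requires every failure before Day 35 to lack a Day 35 value, which the filing rule in SAP 4.3 and 6.2 does not produce but the literal wording of SAP 2.1 would. All these figures assume SD 2.5 and 38 per arm, concern the PP test alone, and take no credit for FAS confirmation.

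This is an inexpensive gap to close before unblinding. It does not invalidate the primary analysis, and it is unlikely to change the conclusion unless the upper bound falls close to 2.

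**What to change.** 1. **SAP 6.7.1, before unblinding.** Add a sensitivity ANCOVA with the same model and the same 2-point limit, in the FAS and in the PP set with these patients retained. It applies to patients in either arm withdrawn before Day 35 for an adverse event or lack of performance who have no assessment at, or filed to, Day 35. Each gets the worse of zero change and the change at the withdrawal visit. Actual Day 35 scores, and scores filed to Day 35, are not overwritten. Cost: one extra model on data already collected. Downside: the imputation is deliberately conservative (an adverse-event withdrawal whose staining had improved is scored as no change), so it supports the primary analysis and does not replace it.

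2. **SAP 2.1 against SAP 4.3 and 6.2.** Reconcile the two filing rules and state one before the blind review meeting, because the rule decides whether a withdrawal score counts as Day 35. Cost: a wording correction.

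3. **Future studies only.** Consider keeping the Day 35 Oxford grading for consenting patients who stop the product, with clinical management left to the investigator. It looks too late here: the SAP reports 101 randomised and describes the conduct of the investigation in the past tense.

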6.7.4 Point of enrolment

Patients are to be enrolled at about 35 investigational sites in France, Spain, Slovakia and Poland.

6.7.5 Total expected duration of the clinical investigation

This investigation is planned to start in October 2018 and to be completed in December 2020.

